- Next, the study team member will place the HR and GSR device on the individual's non-writing hand and begin 306 monitoring. The participant will then begin the writing exposure and tDCS device will be activated. The Soterix 307 device has standardized programming so that all participants receive the same dose (or sham) and intervention 308 based on the set procedures. The tDCS device will be set at 2.0mA for a total of 30-minutes. Once the "start" 309 button is clicked by the study team member, the device is programmed to gradually ramp up current to the set 310 intensity dose (2.0mA in this study) in the first 30-seconds. As seen in Figure 1, in the active intervention the 311 current will remain at 2.0mA for 30-minutes and then the programmed device will gradually ramp down from 312 2.0mA to 0.0mA in the final 30-seconds. 313

Figure 1. tDCS active condition

As seen in Figure 2, during sham stimulation, participants will experience the gradual current ramp up from 0.0 mA to 2.0mA in the first 30-seconds and then a gradual ramp down from 2.0mA to 0.0mA (30-seconds). The programmed device will automatically repeat this process at the end of the set duration of 30 minutes.

319 Figure 2. tDCS sham condition

320

325

314

315

316

317

318

A study team member will be in the immediate proximity during tDCS (or sham)/written exposure to monitor participant safety and abort the tDCS, if necessary. Clicking the "abort" button will initiate a ramp down of current to 0.0mA. A medical provider will also be available should the participant experience a serious AE or require a higher level of medical care.

56GTSPH3C08UU94FUFQ8ULIG00.docx STRONG STAR Template Version 01/31/22

Title: Safety, feasibility, and benefits of transcranial direct current stimulation (tDCS) in human subjects with PTSD receiving an exposure-based, behavioral therapy

• Following the tDCS (or sham) and writing, a study team member will remove the tDCS and HR/GSR device. Consistent with WET, the participant will meet with a study therapist to review their writing for 15-30 minutes. During this time, the participant will also be monitored for safety prior to leaving the appointment.

7.3.1 Collection of Human Biological Specimens. Females will complete a CLIA-waived hCG pregnancy test at baseline for
 screening eligibility purposes.

332

326

327 328

329

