Assessment timepoints are presented in the 7.3 Table. The PCL-5 will be the primary outcome to evaluate changes in 432 PTSD severity from baseline assessment to one-month follow-up, with data points collected during treatment also 433 included in models (Aim 3a). Heart rate monitoring and GSR will be used to evaluate physiological stress arousal during 434 435 the writing exposure task (Aim 3b). Both physiological outcomes will be collected during the writing exposure portion of sessions 1, 3, and 5 to provide before, after, and peak estimates of physiological arousal. Time points of interest for 436 437 physiological outcomes will be the immediate, long-term, and peak effects of tDCS. The immediate effect of tDCS will be 438 defined as changes immediately prior to and after the first written exposure (i.e., change from T_1 to T_2), the third written 439 exposure (change from T_3 to T_4), and the last time participants engage in writing exposure (change from T_5 to T_6). The 440 long-term effect of tDCS will be defined as changes in physiological levels across sessions (session 1 to session 5) prior 441 to engaging in the writing exposure (change from T_1 to T_5) and after the writing exposure (change from T_2 to T_6). The *peak* effect will evaluate change score differences (interaction effect) in the greatest estimate during session 1 to session 5. 442

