 25. Heart Rate. Heart rate will be assessed using a wearable Fitbit wrist watch device. Heart rate data can be beneficial for individuals who report subjectively being more aroused during the exposure or behaviorally appear to be more activated. Heart rate was selected because it is a robust physiological factor associated with PTSD and stress that can be measured affordably and without specialized expertise. Heart rate will be assessed continuously during the written exposure portion of sessions 1, 3, and 5.
- 855
 26. Galvanic Skin Response. GSR will be assessed using a wearable Fitbit wrist watch device. GSR data can also be
 beneficial for individuals who report subjectively being more aroused during the exposure or behaviorally appear to be
 more activated. GSR was selected because it is a robust physiological factor associated with PTSD and stress that
 can be measured affordably and without specialized expertise. GSR will be tracked using a wearable device to assess
 the pre, post, and peak arousal levels during session. GSR will be assessed continuously during the written exposure
 portion of sessions 1, 3, and 5.
- 27. hCG Pregnancy Test. Pregnancy will be assessed at the baseline appointment using a human chorionic gonadotropin
 (hCG), CLIA-waived pregnancy test. hCG pregnancy tests are a reliable and valid measure of pregnancy that
 evaluates hCG levels in the blood or urine and can determine whether a person is pregnant, as well as whether their
 body is producing the right level of pregnancy hormones.

867 868 869 15.0 REFERENCES.

- Ahmadizadeh, M. J., Rezaei, M., & Fitzgerald, P. B. (2019). Transcranial direct current stimulation (tDCS) for post traumatic stress disorder (PTSD): A randomized, double-blinded, controlled trial. *Brain Research Bulletin*, *153*, 273–
 278. https://doi.org/10.1016/j.brainresbull.2019.09.011
- Amtmann DA, Cook KF, Jensen MP, Chen W-H, Choi SW, Revicki D, Cella D, Rothrock N, Keefe F, Callahan L, Lai J-S
 (2010). Development of a PROMIS item bank to measure pain interference. *Pain 150*(1):173-82.
 functioning in returning veterans. *Journal of Anxiety Disorders*, *28*(3), 310–317.
 https://doi.org/10.1016/i.janxdis.2014.01.005
- Benjet, C., Bromet, E., Karam, E. G., Kessler, R. C., McLaughlin, K. A., Ruscio, A. M., Shahly, V., Stein, D. J., Petukhova,

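### The sections disagree on when HR and GSR are recorded: no post-writing recording is planned for T2, T4 and T6, and the pre-writing signal behind T1, T3 and T5 has no stated length or rest period

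*Combined protocol and SAP*

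**What the plan says.** Section 7.4.3 sets out three physiological effects for Aim 3b.

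- **Immediate:** "changes immediately prior to and after the first written exposure" (T1 to T2), and likewise for the third exposure (T3 to T4) and the last (T5 to T6).
- **Long-term:** session 1 to session 5, once on pre-writing values (T1 to T5) and once on post-writing values (T2 to T6).
- **Peak:** the change in the greatest value from session 1 to session 5.

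Three places describe the recording period.

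- **Section 7.4.3:** "Both physiological outcomes will be collected during the writing exposure portion of sessions 1, 3, and 5 to provide before, after, and peak estimates".
- **Section 14.3, item 25:** "Heart rate will be assessed continuously during the written exposure portion of sessions 1, 3, and 5". Item 26 sets the same limit for GSR, although it also names pre, post and peak levels as the target.
- **Section 7.3:** staff fit the device to the non-writing hand and start monitoring. Then: "The participant will then begin the writing exposure and tDCS device will be activated". At the end: "Following the tDCS (or sham) and writing, a study team member will remove the tDCS and HR/GSR device". The therapist review comes next.

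The note to the study flow figure, just before Section 6, says the devices are worn during sessions 1, 3 and 5 and does not limit this to the writing. No section gives a window length, a rest period, a summary statistic or a time-stamping rule for T1 to T6.

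**The concern.** A record limited to the writing holds no value from before it and none from after it, yet most of the planned contrasts are built on such values. Section 7.3 eases this at the start, where some monitoring precedes the writing, but not at the end, where removal is the next listed step.

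Staff who follow the text, and whoever later analyses the data, must improvise. The obvious substitutes are the first and last stretch of the writing. An early-writing value already contains some response to the exposure and the start of stimulation. A late-writing value is still within the task and may overlap ramping. The immediate effect would then be a start-to-end change within the task, not the pre-to-post change that the plan defines.

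This is more than missing detail that an analysis plan could supply later, because signal that was never recorded cannot be recovered. It also touches what the pilot is for: Section 7.4.3 wants effect sizes and data-analysis lessons to carry into a larger trial.

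**Working it through.** The plan states no figure for HR or GSR (no power, effect size or window length), so there is nothing to reproduce. The check sets the sections side by side and does simple timeline arithmetic.

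1. **Contrasts affected (Section 7.4.3).** Before/after contrasts per signal: 3 immediate + 2 long-term = 5. Those that need an after value: T1–T2, T3–T4, T5–T6 and T2–T6, that is 3 + 1 = 4 of 5. The remaining one, T1–T5, needs only pre-writing values. The peak contrast needs neither.

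2. **Start of the record (Section 7.3).** The order is device on, monitoring begins, then writing and current begin. The pre-writing record is therefore longer than zero, with its length unstated and no rest period. Sections 7.4.3 and 14.3, read literally, would not collect it.

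3. **If early writing stands in for the pre value (Section 7.3).** In the first 30 seconds both arms ramp up to 2.0 mA. In the next 30 seconds the active arm stays at 2.0 mA while sham ramps down. A value from the first minute would come after stimulation has begun, and for the second half of that minute the arms receive different current.

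4. **End of the record (Section 7.3).** Section 7.3 gives the device time as 30 minutes in total. It also describes 30 minutes at 2.0 mA with a 30-second ramp on each side, which would be 0.5 + 30 + 0.5 = 31 minutes. If writing and current start together and writing lasts 30 minutes, stimulation ends 30 − 30 = 0 to 31 − 30 = 1 minute after the writing. Any signal caught in that gap would include the active ramp-down or sham's repeated ramp up and down. No later recording is planned.

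5. **Lead-in to T1 and T5 (Section 7.3).** In session 1, about 30–45 minutes of psychoeducation precede set-up and writing. Session 5 opens with the writing. Both arms share this difference, so it should cancel on average in the treatment-by-time interaction. It does not cancel in the within-arm changes over time that Section 7.4.3 also plans.

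6. **Room in the sessions (Section 7.3).** Slack = stated length − allotted activities.
 - Sessions 2–5: 60 − (30 + 15) = 15 down to 60 − (30 + 30) = 0 minutes.
 - Session 1: 90 − (30 + 30 + 15) = 15 down to 90 − (45 + 30 + 30) = −15 minutes.
 - With 10 added minutes: 5 to −10 in sessions 3 and 5, and 5 to −25 in session 1.

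**The case against.** The strongest reply is that Section 7.3 starts monitoring before both writing and current, so T1, T3 and T5 can be taken as defined and T1–T5 compares unstimulated values. The figure note and item 26 point the same way. The writing portion may also be read loosely, as the part of the session that includes its set-up. On that reading the sections largely agree for the pre-writing values. This stands: a reader might infer that nothing outside the writing is recorded and that none of T1 to T6 can be derived, and the documents do not support that. Nor do they say that the pre-writing signal lasts only seconds, or that T1–T5 is contaminated by stimulation.

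For the post-writing values, removal follows stimulation and writing with no stated delay, so some signal may be caught. That also stands: it is a gap in the plan, not a proven impossibility. But an incidental signal of unknown length, possibly overlapping a ramp, is not a planned measurement.

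Finally, Aim 3b is exploratory, the pilot is openly unpowered, and safety, feasibility, the PCL-5 and the peak measure are unaffected. This limits the severity. It does not remove the point, because the same section gives informing a larger trial as the reason for these analyses.

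**Conclusion.** The point holds as an inconsistency between sections with a definite gap at the end of the record. Four of the five before/after contrasts for each signal depend on after values for which no matching recording period is planned. The fifth depends on a pre-writing signal of unspecified length, without rest, that follows different lead-ins in sessions 1 and 5.

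No size of bias can be given. A reader might assume that the arousal response has reached some fraction f of its full size in the window used as the pre value, and conclude that the change is understated by f. The documents give no value for f, so the result only restates the assumption. It also requires arousal to be at its full size at the end, which need not be so if arousal falls during the writing. A comparison of randomised arms on a within-task change would still be a fair comparison, but of a different quantity from the one defined.

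The conclusion rests on taking the order of steps in Section 7.3 as written. The timing in step 4 of the working also assumes that writing lasts 30 minutes and starts with the current. This is a cheap improvement worth making before HR and GSR are collected. It does not threaten the trial's main aims.

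**What to change.** Reconcile Sections 7.3, 7.4.3 and 14.3 (items 25 and 26) so that they give one recording period. Then:

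- Start the record with a fixed, quiet, seated period after electrodes and device are in place and before writing or current begins.
- Leave the device on for a fixed short period after both the writing and the final ramp have ended, then remove it.
- Define T1, T3 and T5 as the mean over the first window and T2, T4 and T6 as the mean over the second, excluding ramp periods. Time-stamp the start and end of writing and of current.
- Settle in Section 7.3 whether the ramps fall inside or outside the 30 minutes, so that the second window has a clear start.

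Up to 5 minutes per window is an example; the length should be chosen to fit the session. Stimulation and therapy content do not change, and the device and staff are already in place.

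The cost is protocol wording and up to about 10 extra minutes in sessions 1, 3 and 5. Given the slack of 0 to 15 minutes in sessions 3 and 5 and −15 to 15 minutes in session 1, some visits may overrun their stated length. The second window also puts a short wait between the writing and the therapist review, which the investigators should weigh when choosing its length.

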- Aim 3: To explore PTSD symptom reductions associated with tDCS vs. sham when combined with WET. 33
- Hypothesis 2: tDCS can reduce PTSD severity more so than a sham condition when combined with WET for PTSD 34 on the PTSD Checklist (PCL-5). 35
- Hypothesis 3: tDCS can decrease physiological arousal (heart rate and galvanic skin response) associated with the 36 stress response during written exposure. 37
- 38 39 4. MILITARY RELEVANCE.

40 The proposed study will recruit civilians and military veterans seeking PTSD treatment. Although this study will recruit a 41 mixed sample of civilians and veterans, findings from this study can inform existing literature focused on military-related 42 PTSD. Compared to civilians, the rate of PTSD is particularly elevated among military populations, with approximately 43 23% of military vs. 6-8% of civilians meeting criteria for PTSD (Fulton et al., 2015). Furthermore, PTSD has been identified as the signature deployment-related psychiatric condition among service members. The functional impact of 44 PTSD can cost service members their military careers and veterans with PTSD are at increased risk of unemployment 45 and homelessness following military separation (Asnaani et al., 2014). Notwithstanding evidence that current first-line 46 47 treatments are effective for PTSD, there remains room for improvement in outcomes given that a large proportion of patients (~50%) do not significantly benefit from treatment (Steenkamp et al., 2015b). Research dedicated to evaluating 48 novel treatments for PTSD has the potential to promote greater PTSD treatment efficacy that will lead to greater symptom 49 reductions, positive well-being, and improved functioning in the military community. 50 51

5. BACKGROUND AND SIGNIFICANCE. 52

53 Impact and Prevalence of PTSD: Approximately, 70% of the U.S. population (~232 million) will experience a traumatic event in their lifetime and 7% of those individuals (~16 million) will go on to develop PTSD (Benjet et al., 2016). Symptoms 54 55 of PTSD can include fear, anxiety, negative mood, uncontrollable/negative thoughts about the event, sleep disturbances, 56 and avoidance of environmental trauma reminders. The impact of PTSD is substantial and often results in chronic,

56GTSPH3C08UU94FUFQ8ULIG00.docx

STRONG STAR Template Version 01/31/22

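### Hypothesis 3 concerns arousal during written exposure, but the named HR and GSR contrasts use before, after and peak-change values that can miss a reduction confined to the writing period

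*Combined protocol and SAP*

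**What the plan says.** Hypothesis 3 (section 3) reads "tDCS can decrease physiological arousal (heart rate and galvanic skin response) associated with the" "stress response during written exposure". Section 7.4.3 gives Aim 3b the same target: "Heart rate monitoring and GSR will be used to evaluate physiological stress arousal during" the writing task. Section 14.3 describes the recording: "Heart rate will be assessed continuously during the written exposure portion" of sessions 1, 3 and 5, with the same statement for GSR.

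Section 7.4.3 then says that the recording will supply before, after and peak estimates, and names three kinds of effect:

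- Immediate: "defined as changes immediately prior to and after the first written exposure" (T1 to T2), then the third "exposure (change from T_3 to T_4), and the last time participants engage in writing exposure (change from T_5 to T_6").
- Long-term: T1 to T5 (before values) and T2 to T6 (after values).
- Peak: the difference between arms in the change of the greatest value from session 1 to session 5.

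No mean, area under the curve or time course over the writing period is specified. The general model text in section 7.4.3 adds simple effects of treatment at each time point, without saying which HR and GSR values count as time points.

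On the recording window, section 7.3 has staff place the device and begin monitoring before writing starts. After stimulation and writing, "a study team member will remove the tDCS and HR/GSR device". Neither a pre-writing nor a post-writing recording length is given.

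**The concern.** The hypothesis concerns the level of arousal while the participant writes under stimulation. Most of the named contrasts look at the two ends of that period. The only one that draws on the period itself, the peak, is differenced between two sessions in which the active arm is stimulated both times.

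Two plausible patterns therefore go largely unseen. If arousal rises and settles within the 30 minutes, after minus before is small in both arms whatever tDCS did in between. If tDCS lowers arousal by about the same amount in every session, the session 1 to session 5 change in peak has an expected arm difference of zero. The pilot is meant to supply effect sizes (Hedges' g with 95% limits) for planning a larger trial. An effect size from a contrast that cannot register the hypothesised effect is a poor guide for that, when the data for a better one are already being collected.

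**Working it through.** **1. Count of named contrasts.** The documents give no total, so there is no stated figure to reproduce. From section 7.4.3, per signal: 3 immediate (T1–T2, T3–T4, T5–T6) + 2 long-term (T1–T5, T2–T6) + 1 peak change = 6. Two signals give 6 × 2 = 12. Before/after only: 5 × 2 = 10. Peak change: 1 × 2 = 2. No peak contrast is named for session 3.

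**2. What the peak change estimates.** Let Δ1 and Δ5 be the arm differences in peak at sessions 1 and 5. The contrast is Δ5 − Δ1. If Δ1 = Δ5 = Δ, it is 0 for any Δ. It asks whether the effect grows between sessions, not whether it is present. The assessment table in section 7.3 shows tDCS or sham at every session from 1 to 5, so an equal effect is a natural reading of Hypothesis 3.

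**3. What after minus before registers.** All inputs here are assumptions; none is in the documents. They are 20 per arm, mean HR response 10 bpm (SD 5), 30% cut under tDCS, one-minute noise SD 4 bpm, lag-one autocorrelation 0.7, one pre-writing minute, 30 writing minutes, one post-writing minute, and linear decay of the response to a fraction e at the end of writing.

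- Response variance averaged over arms: (25 + 0.7² × 25)/2 = 18.625.
- After minus before: difference 3e bpm, SD √(2 × 16 + 18.625e²).
- During-writing mean minus before: with m = (1 + e)/2, difference 3m bpm, SD √(16.26 + 18.625m²). The noise term is 16 + 2.746 − 2 × 1.244 = 16.26, where 2.746 is the variance of the 30-minute mean and 1.244 its covariance with the pre-writing minute.

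| Response at end of writing | After minus before | During mean minus before |
|---|---|---|
| 20% | 0.6/5.72 = 0.10 | 1.8/4.79 = 0.38 |
| 50% | 1.5/6.05 = 0.25 | 2.25/5.17 = 0.44 |
| Sustained | 3.0/7.11 = 0.42 | 3.0/5.91 = 0.51 |

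**4. The same calculation with a tDCS effect that builds linearly from 0 to 30% over the 30 minutes.**

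| Response at end of writing | After minus before | During mean minus before |
|---|---|---|
| 20% | 0.6/5.72 = 0.10 | 0.69/4.93 = 0.14 |
| 50% | 1.5/6.05 = 0.25 | 0.99/5.35 = 0.19 |
| Sustained | 3.0/7.11 = 0.42 | 1.5/6.15 = 0.24 |

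The ranking reverses in the last two rows.

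**5. Extreme case by simulation.** Assumptions: 20 per arm, arousal 0.8 SD lower throughout writing in both sessions, no effect just before or after, between-session correlation 0.5, two-sided 0.05, 4,000 runs. Rejection rates were 4.7% for T1–T2, 4.7% for T1–T5, 5.4% for T2–T6 and 4.5% for the peak change, all at the null level. An arm comparison within session 1 gave 69% for the during-writing mean and 67% for the peak. The null-level results follow from how the case is built; it shows that all the named types of contrast can be blind at once.

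**The case against.** Several points on the other side have force.

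- *Hypothesis 3 is not left untested.* Peak is a during-writing value, and the generic simple effects could yield a within-session arm comparison. That stands in part: it would help only if peak were entered as a time point, and the plan does not say so.
- *Before and after may be the edges of the writing record.* Section 7.4.3 says the values are collected during the writing portion, and section 14.3 speaks of pre, post and peak levels during the session. On that reading the 10 contrasts still use only the two ends. The ambiguity is a reason to define the windows.
- *Pre-writing recording exists.* A reader might infer from section 14.3 that T1, T3 and T5 cannot be obtained. Section 7.3 starts monitoring before writing, so what is missing is a window length. Post-writing recording is unspecified rather than ruled out.
- *The during-writing mean is not always the better measure.* A reader might infer that from step 3. Step 4 shows the opposite for an effect that builds up over a sustained or half-decayed response. On the step 3 assumptions, simulation of a within-session peak minus before gave 0.46 to 0.49, above the mean in both decay cases. The documents give no HR or GSR time course, so there is no basis for replacing the planned contrasts.
- *This is a pilot.* A reader might infer that a null result would count against the mechanism. Section 7.4.3 states that the study is not powered for mechanistic testing and reports effect sizes with intervals, so that inference is not supported. The same section also commits to analyses suited to an adequately powered study in order to inform planning, which is a reason to name the relevant contrast now.

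**Conclusion.** The concern holds as a gap between the hypothesis and its named contrasts. Ten of 12 use before and after values only, and the other two have expectation zero when the reduction is the same in sessions 1 and 5. Those two statements follow from the documents and simple algebra, and need no assumed effect size.

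The size of the loss is not known. On the assumed values, with an immediate and constant tDCS effect, the standardised difference for after minus before runs from 0.10 to 0.42 as the response goes from largely settled to sustained, against 0.38 to 0.51 for the during-writing mean. With an effect that builds up, before/after can be the stronger measure. The conclusion is therefore to add a during-writing summary, not to put it in place of what is planned. This is an inexpensive improvement to an exploratory aim, and it does not call the safety, feasibility or PCL-5 analyses into question.

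**What to change.** Before unblinding, amend the Aim 3b text in section 7.4.3:

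1. Define a during-writing summary for HR and for GSR at sessions 1, 3 and 5: the mean or area under the curve over the writing period, adjusted for the pre-writing value. Choose one of the two in advance.
2. Estimate the arm difference in that summary within each of the three sessions in the planned mixed model, and name it a key Aim 3b contrast alongside the before/after and peak-change contrasts.
3. Add a within-session arm comparison of peak, with peak defined as the highest one-minute mean so that a single artefact cannot set it.
4. Fix the length and position of the T1 to T6 windows. Include a short post-writing recording before the device is removed, and align sections 7.3, 7.4.3 and 14.3.

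Cost: one more derived variable per signal, a few recording minutes at three sessions, and a larger Benjamini-Hochberg family. If every session-specific comparison is counted, the named Aim 3b contrasts go from 12 to 12 + 3 × 2 (during-writing) + 3 × 2 (peak) = 24, so the text should say which of them are in the adjusted family. The during-writing data are already collected.
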